9.2 Participant Exclusion Criteria

Candidates will be excluded if ANY of the following criteria apply:

1. Structural heart defect which can only be repaired by cardiac surgery
2. Pericarditis within 6 months
3. LVEF \leq 25% for VT patients
4. LVEF \leq 40% for patients with atrial arrhythmia
5. History of chronic gastro-intestinal medical problems involving the esophagus, stomach and/or untreated acid reflux
6. History of abnormal bleeding and/or clotting disorder.
7. Clinically significant infection or sepsis
8. History of stroke or TIA within the past 6 months of enrollment
9. Uncontrolled heart failure or NYHA function class IV
10. Implanted with a pacemaker or intracardiac cardiac defibrillator within the past 6 weeks (42 days)
11. Implanted with a mechanical valve
12. Diagnosed atrial or ventricular myxoma, interatrial baffle or patch, tumor or other abnormality that precludes catheter introduction or manipulation.

13. Any of the following within 6 months of enrollment
 - a) Major surgery except for the index procedure
 - b) Myocardial infarction
 - c) Unstable angina
 - d) Percutaneous coronary intervention (e.g. CABG or PTCA)
14. Patients with any other significant uncontrolled or unstable medical condition (such as uncontrolled bradyarrhythmia's, ventricular arrhythmias, hyperthyroidism, or significant coagulation disorder)
15. Significant congenital anomaly or medical problem that in the opinion of the investigator would preclude enrollment in this study.
16. Women who are pregnant (as evidenced by pregnancy test if pre-menopausal), lactating, or who are of childbearing age and plan on becoming pregnant during the course of the clinical investigation.
17. Categorized as vulnerable population and requires special treatment with respect to safeguards of well-being.
18. Concurrent enrollment in an investigational study evaluating another device or drug.

10. Participant Withdrawal or Termination

10.1 Reasons for Withdrawal or Termination

Participants are free to withdraw from participation in the study at any time upon request without penalty or loss of benefits to which they may otherwise be entitled. Participants will be informed prior to study entry that they are free to withdraw from the study at any time and for any reason without prejudice to their future medical care by a physician or the institution.

An investigator may terminate a subject's participation in the study if:

- Any clinical AE, laboratory abnormality, or other medical condition or situation occurs such that continued participation in the study would not be in the best interest of the participant
- Withdrawal is in the subjects' best interest
- Subject withdraws consent
- Subject is lost to follow-up

Every subject should be encouraged to remain in the study until they have completed the protocol required follow-up period.

10.2 Handling of Participant Withdrawals or Termination

If a subject is removed or withdraws from the study, the date and reason for withdrawal will be recorded on the appropriate electronic Case Report Form (eCRF). If the subject withdraws consent PRIOR to insertion of the study catheter, the subject can be replaced. If the subject is withdrawn due to an AE or SAE, the Investigator should follow the subject until the AE/SAE has resolved or is considered stable or until the participant has been deemed lost to follow-up after demonstration of due diligence of follow-up efforts.

If a subject is unable to return for an office/clinic visit or cannot be contacted by telephone, 3 separate telephone calls should be made to obtain subject related safety information. All attempts should be documented in the source documents. If the subject does not respond to the 3 telephone calls, then the investigator must send a certified letter to the subject. If the

subject does not respond to the letter, then the subject will be considered “lost to follow-up” for the study.

Subjects who have signed the ICF, but are later found not to be eligible PRIOR to insertion of the study catheter can be replaced. Replacement subjects will be recruited and enrolled following the same procedures as non-replacement subjects.

All applicable case report forms up to the point of subject withdrawal must be completed. Data collected up to the point of subject withdrawal may be used, unless local regulations apply.

10.3 Subject Disposition

- **Enrolled Subjects:** Patients who sign the ICF.
- **Excluded Subjects:** Subjects who are enrolled but never undergo insertion of the study catheter. Excluded subjects will be subjected to safety event reporting between ICF signature and date of exclusion. Subjects who signed the ICF but are found to be ineligible prior to insertion of the catheter are also considered as excluded.
- **Discontinued Subjects:** Enrolled subjects who have the study catheter inserted but no assessments are performed with it. Discontinued subjects will remain in follow-up for 7 days for safety evaluation.
- **Lost to Follow-up Subjects:** Enrolled subjects of which contact is lost after most recent visit (despite 3 documented attempts to contact the subject).
- **Withdrawn / Early Termination Subjects:** Subjects who withdraw consent for study participation or are withdrawn by the investigator, are terminated from the study prior to completion of all follow-up visits.
- **Completed Subjects:** Enrolled subjects who have not been excluded, discontinued, withdrawn, terminated early, or lost-to-follow-up from the study prior to the final study visit.

11. Responsibilities

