14.2.2 Study Procedure

Subjects will arrive to the electrophysiology laboratory for their study procedure and will undergo preparation for the procedure per the hospital's standard protocol (discretion of investigator)

Overall Use of the Investigational Device

During study procedures, investigators will use the investigational catheter instead of the institution's standard ultrasound catheter choice (e.g. SOUNDSTAR™). Any use of a non-investigational ultrasound device will be considered a failure of the primary performance endpoint.

The use of the investigational NUVISION™ NAV Ultrasound Catheter is **mandatory** for:

- Thrombus detection and LA/LV imaging for volume measurement at the start of the procedure;
- During transeptal puncture;
- And as navigational ULS catheter throughout the procedure.

Imaging guidance for LA/LV volume measurements:

- Capture preferably the full chamber in one ULS volumetric segment, if needed several segments can be taken.
- For capturing of the LA:
 - Capture 4D ULS clip (full 90°x90°) of the LA (with PVs and LAA) taken from the RA.
 - Repeat the acquisition from 3-6 slightly different positions, where the LA volume is partial.
Note: Capture 4D ULS clip before transeptal and insertion of any other catheters to the LA, by using the default ULS settings, and without using the "zoom" function.
 - Place the investigational NUVISION™ NAV Ultrasound Catheter near the interatrial septum and make sure to capture the ENTIRE left atrium.
 - Confirm by seeing both anterior-posterior and Roof to Mitral valve planes.
 - Make sure to allow sufficient ULS depth by visualizing the distal LAA.
- For capturing of the LV:
 - The catheter can be positioned either in the RA near the inferior septum or in the right ventricle (RV) near the interventricular septum.
 - Make sure to allow sufficient ULS depth by visualizing the entire chamber from the Mitral valve to the distal apex.

Investigators should use the CARTO™ 3 system to **"bookmark"** instances of abnormal study catheter "imaging noises". This will allow for further analysis of the data.

Standard of Care Ablation Procedure

Treatment will be per institution's standard of care (SOC).

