20.3 Analysis Sets

Safety Analysis Set: The Safety Analysis Set will consist of all enrolled subjects who have undergone insertion of the NUVISION™ NAV Ultrasound catheter.

Per Protocol (PP) Analysis Set: The PP Analysis Set will include all enrolled subjects who met the study eligibility criteria and in whom assessments were performed with the NUVISION™ NAV Ultrasound catheter.

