20.4.6 Analysis for Primary Endpoints

Primary Performance Endpoint is defined as the completion of imaging required for the study procedure with the NUVISION™ NAV Ultrasound Catheter without resort to non-study ultrasound device(s).

The number of subjects who successfully completed the procedure without resort to a non-study ultrasound device will be summarized overall and per procedure type (atrial ablation/ventricular ablation) for the PP Analysis Set.

A listing of the primary performance endpoint will be provided.

Primary Safety Endpoint is defined as the occurrence of serious adverse events related to the Investigational catheter within 7 days of index procedure. An SAE will be counted as related to the investigational catheter if the relationship to a study catheter is anything other than 'Not Related'.

The number of subjects with SAEs related to the investigational catheter will be summarized in the Safety Analysis Set overall and per procedure type (atrial ablation/ventricular ablation) by System Organ Class and Preferred Term and level of relationship. All tables will present summaries both by subject and by event. If a subject has multiple occurrences of an event within a level of summarization, then for the by-subject summaries only a single occurrence will be counted at each level of summarization at the highest level of severity/relationship; for the by-event summary all events will be counted.

All investigational catheter related SAEs will be listed by System Organ Class and Preferred Term, severity, causality (defined as possible, probable or having a causal relationship to the device and/or procedure), anticipation and outcome.

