## 6 Analysis Sets

Safety Analysis Set: The Safety Analysis Set will consist of all enrolled subjects who have undergone insertion of the NUVISION™ NAV Ultrasound catheter.

**Per Protocol (PP) Analysis Set**: The PP Analysis Set will include all enrolled subjects who met the study eligibility criteria and in whom assessments were performed with the NUVISION™ NAV Ultrasound catheter.

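### An eligible subject in whom a study-device fault prevents any insertion of the study catheter drops out of the primary performance percentage, although a switch to another ultrasound device is defined as a failure

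*Protocol*

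**What the plan says.** **Disposition.** Protocol 10.3 defines Excluded by non-insertion alone: "Subjects who are enrolled but never undergo insertion of the study catheter". Subjects found ineligible before insertion are added to that category, so ineligibility does not limit the main definition. Discontinued is a different category, for subjects who had the catheter inserted but no assessments made with it.

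**Replacement.** Protocol 10.2 allows replacement before insertion on two grounds. One is consent: "If the subject withdraws consent PRIOR to insertion of the study catheter, the subject can be replaced". The other is ineligibility. A device fault is not named.

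**Analysis sets.** There are two, worded alike in Protocol 20.3 and SAP 6. For safety: "The Safety Analysis Set will consist of all enrolled subjects who have undergone insertion of the NUVISION™ NAV Ultrasound catheter". The PP set takes "all enrolled subjects who met the study eligibility criteria and in whom assessments were performed with the NUVISION™ NAV Ultrasound catheter".

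**Primary performance endpoint.** Success means that the imaging the procedure needs is finished with the study catheter and with no other ultrasound device. Protocol 14.2.2 adds: "Any use of a non-investigational ultrasound device will be considered a failure of the primary performance endpoint". The synopsis carries the same rule, there calling the endpoint effectiveness. Under Protocol 20.4.6 the result "will be summarized overall and per procedure type (atrial ablation/ventricular ablation) for the PP Analysis Set". SAP 8.5 uses the same set.

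**Safety reporting.** Protocol 10.3 states: "Excluded subjects will be subjected to safety event reporting between ICF signature and date of exclusion". For the other category it states: "Discontinued subjects will remain in follow-up for 7 days for safety evaluation".

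**The concern.** A catheter or connector cable that proves faulty at set-up is a device failure in the ordinary sense. If the site then does the case with its usual ultrasound catheter, Protocol 14.2.2 calls that a performance failure and does not require that the study catheter was inserted first. The population rules nevertheless remove the subject before the endpoint is calculated. Numerator and denominator are both restricted to subjects in whom the device got far enough to be used.

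The effect can only favour the device: each such case leaves the reported rate unchanged or raises it. That matters in a first-in-human study whose stated purpose (Protocol 7.2) is to judge safety and feasibility for further development, and in which the connector cable to the ultrasound console is itself investigational.

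The gap is separate from that of the Discontinued subjects, who are also outside the PP set. Moving the performance analysis to the Safety set would recover Discontinued subjects, because they had an insertion. It would not recover these.

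**Working it through.** The plan has no figure to reproduce. The 30 subjects rest on previous experience, with no assumed rate, precision target or power. The check is a trace through the definitions, then an illustration of size.

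**Trace.** Take an eligible, consented subject. The study catheter is opened or connected, a study-device deficiency prevents insertion, no second study catheter is inserted, and the site uses its standard ultrasound catheter.

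1. Disposition (Protocol 10.3): no insertion, so Excluded.
2. Safety set (Protocol 20.3, SAP 6): requires insertion, so not included.
3. PP set (same sections): requires assessments with the catheter, so not included.
4. Outcome rule (Protocol 14.2.2, synopsis): another ultrasound device was used, so a failure.
5. Primary performance analysis (Protocol 20.4.6, SAP 8.5): PP set only, so the failure in step 4 does not enter.
6. Elsewhere: the disposition summary and listing cover all subjects (Protocol 20.4.3, SAP 8.2), and the device-deficiency listing names no analysis set (Protocol 20.4.7, SAP 8.6). The case appears there.

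**Size.** Inputs: 30 enrolled subjects (Protocol 20.2) and the two-sided 95% level (Protocol 20.1). Assumptions: k pre-insertion failures as traced above, all other subjects eligible and successful, no replacement. The value of k is not in the documents.

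- Rate as planned: (30 − k)/(30 − k).
- Rate with these cases counted: (30 − k)/30.
- Exact (Clopper-Pearson) limits for x successes in n: lower = 0.025 quantile of Beta(x, n − x + 1); upper = 0.975 quantile of Beta(x + 1, n − x). When x = n, the lower limit is 0.025^(1/n) and the upper is 100%. The plan names no interval for this endpoint; the method is my choice.

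| k | As planned (95% CI) | Counted as failures (95% CI) |
|---|---|---|
| 0 | 30/30 = 100% (88.4 to 100) | 30/30 = 100% (88.4 to 100) |
| 1 | 29/29 = 100% (88.1 to 100) | 29/30 = 96.7% (82.8 to 99.9) |
| 2 | 28/28 = 100% (87.7 to 100) | 28/30 = 93.3% (77.9 to 99.2) |
| 3 | 27/27 = 100% (87.2 to 100) | 27/30 = 90.0% (73.5 to 97.9) |

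Each case moves the point estimate by 1/30, or 3.3 percentage points. If such subjects were replaced, which Protocol 10.2 does not provide for, the contrast would be 30/30 against 30/31 = 96.8% (83.3 to 99.9) for k = 1.

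**How likely is at least one?** With a true pre-insertion failure rate p, the chance is 1 − (1 − p)^30. For assumed p of 1%, 2% and 5% this gives 26%, 45% and 79%.

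**The case against.** **The case is not lost from the report.** This stands. Besides the disposition and deficiency listings, Protocol 15.4.4 requires every device deficiency to be reported within 72 hours, and 18.3 sends suspected malfunctions to complaint analysis. A reader might infer that the failure is counted nowhere, and that is wrong. But neither listing corrects the primary percentage.

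**An outcome rule and a population rule can coexist.** This also stands. Protocol 14.2.2 says what a failure is; 20.3 and 20.4.6 say who is analysed. The fault is the choice of population, which leaves out a case that the outcome rule was written to catch.

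**The scenario is inferred.** True. The documents do not describe it and give no support for a view that faults tend to show at set-up. If a second study catheter is inserted and used, an eligible subject is in both sets and the point does not arise. Nor is the whole CARTO connection under investigation: the synopsis labels the catheter and the connector cable to the ultrasound system as investigational, but not the cable that runs to CARTO.

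**Safety follow-up.** A reader might infer from 10.3 that adverse event reporting certainly stops once the subject is excluded. The documents do not settle that. The date of exclusion is not defined, Protocol 14.3 contacts all subjects at day 7, 15.4.1 collects events to the end of the study, and note 9 to Table 2 sets no end. The subject was also never exposed to the catheter, so absence from the Safety set is ordinary practice.

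**Low stakes.** The study is descriptive, with no test, no performance threshold and no effectiveness claim. That limits the weight, but the percentage is still a primary result.

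**Conclusion.** The point holds for a defined group: eligible enrolled subjects in whom use of the study catheter or investigational connector cable was attempted, but in whom a study-device deficiency meant that no study catheter was ever inserted. They are missing from the primary performance percentage, and the omission can only favour the device.

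The size depends wholly on an unknown count. With none, there is no effect. With one or two in 30 and every other subject successful, a rate of 96.7% or 93.3% would be reported as 100%. The documents do not show that such cases are likely.

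On safety, the conclusion is narrower: Protocol 10.3 and the follow-up and adverse event sections do not agree and must be reconciled. They do not support a claim that safety data will be lost. This is a change the sponsor should make before analysis.

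**What to change.** 1. In Protocol 20.3 and 20.4.6 and SAP 6 and 8.5, analyse the primary performance endpoint in all eligible enrolled subjects in whom study-device use was attempted: study catheter opened or connected, or inserted. Count as a failure any subject whose required imaging was not completed with the study catheter. That includes a device-related switch before insertion and a case finished with no ultrasound at all. Keep the PP analysis as supportive.
2. In Protocol 10.3, limit Excluded to non-insertion for reasons unrelated to the study devices, and add a separate category for device-related non-insertion. Relabelling these subjects Discontinued would not work: that category is defined by insertion, and its members are outside the PP set too.
3. State which rule applies when the catheter was opened and the procedure was then called off for an unrelated reason, since such a subject would be Excluded and yet meet the attempted-use definition.
4. Define the date of exclusion, and reconcile the end of safety reporting in 10.3 with 14.3, note 9 to Table 2 and 15.4.1. The Safety set can stay as it is.

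The cost is wording in both documents. The deficiency eCRF and the device accountability log should already hold most of the data needed. The downside is a performance rate that may be slightly less favourable.

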11.1 Investigator Responsibilities

Investigators at each participating clinical site will have the following responsibilities:

- Assuring compliance by site personnel with the provisions of the protocol
- Providing the Sponsor with:
 - Signed, dated Investigator Agreement
 - Written Ethics Committee (EC) approval letters and EC-approved consent forms
 - Signed, dated Financial Disclosure form for each participating investigator
 - Curriculum vitae for each investigator
- Maintain an accurate and current Delegation of Authority log which identifies individuals authorized to perform work for the study and assuring compliance by site personnel with the provisions of the protocol
- Completing the appropriate training on the device and the Clinical Study Protocol/ Investigational Plan prior to enrolling and using the catheter in subjects
- Maintain accurate and current logs for the study such as:
 - Subject log, Device Accountability Log

- Obtain initial and amendment (if applicable) EC approval and annual review/approval thereafter for the study protocol and informed consent as applicable
- Obtain ICF and enroll patients
- Perform medical procedures
- Order tests required by the study protocol
- Follow subjects until the end of the study protocol
- Accurately complete and sign eCRFs in a timely manner
- Maintain relevant source documentation and allow Sponsor direct access to perform monitoring or auditing duties
- Maintain records and provide reports according to prevailing regulatory requirements
- Share relevant study-related information with delegated study staff
- Inform the appropriate entities (e.g., Sponsor, Competent Authority (CA), EC) in a timely manner regarding the occurrence of AEs and/or product malfunctions.
- Making sufficient effort to maintain contact with treated subjects who fail to comply with the follow-up requirements
- Maintain study records for at least 10 years or as specified per country specific record retention requirements after the study is completed and or terminated. The Sponsor will notify the Investigator of either of these events.
- Complying with EC and Sponsor annual report requirements, including the final report.

11.2 Sponsor Responsibilities

The Sponsor (Biosense Webster, Inc.) will be responsible for the following:

- Conduct of pre-study site assessment and approval
- Preparation and modification (if applicable) of study documents including but not limited to the Clinical Study Protocol/Investigational Plan, CRFs and informed consent
- Selection of appropriately qualified and trained individuals, including monitors, to conduct the study
- Conduct protocol and device training for investigators and research personnel as applicable
- Set-up of study-specific committees (if applicable).
- Obtain signed study contracts from investigators/hospitals, Clinical Research Organizations (CROs) and other involved parties
- Ship study devices to each site
- Monitor sites for the duration of the study
- Maintain study database
- Inform investigator of his/her responsibilities
- Submit and obtain approval for study from applicable regulatory agencies
- Preparation of reports summarizing the status of the study no less than annually. These reports will be supplied to the PI at each site.
- Update Report of Priors, IFU, IB, and Risk Analyses, as applicable
- Update investigators on safety issues, if needed

- Report (including AE's and DDs) to study investigators and regulatory agencies, as required
- Have relevant safety information reviewed by the Study Safety Lead, as required
- Communications with the CA
- Submission of any amendments to the Clinical Study Protocol/Investigational Plan to the CA.
- Maintain study records for at least 10 years or as specified per country specific record retention requirements after the study is completed and or terminated.

12. Study Device Description

12.1 Device Acquisition

After obtaining a fully executed clinical trial agreement and appropriate approvals, the sponsor will initiate shipment(s) of investigational devices to the site. The Sponsor will keep records of all investigational devices shipped to the site. Approved investigational devices will be shipped directly to the site and will be received by the site. Investigators are responsible for appropriate logging of the devices received, verification of packing slip information (i.e., lot numbers and quantity shipped), date and identity that each device was used in the study, disposition information regarding disposal or return to the Sponsor.

